| 

Sleep Disturbance (8b)

CPAQ-8

Catastrophizing

    |             | X                        |                 |                |                                |                |                          |                                | X                              | Х                              |
| PI-NRS daily diaryi  |             | X                        | X               | X              | X                              | X              | X                        | X                              | X                              |                                |
| Adverse event reporting j   |             | $X^k$                    | X               | X              | X                              | X              | X                        | X                              | X                              |                                |
| 

Quantitative sensory test

fMRI

                           |             | X                        |                 |                |                                |                |                          |                                | X                              |                                |
| Wrist actigraphy l  |             | X                        | X               |                |                                |                |                          | X                              | X                              |                                |
| PROMIS-29+2  |             | X                        |                 | X              |                                | X              |                          |                                | X                              | X                              |
| Self-enmeshment task   |             | X                        |                 | X m |                                | X m |                          |                                | X                              |                                |
| Self-Complexity task   |             | X                        |                 |                |                                |                |                          |                                | X                              |                                |

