|--------------|-----------|--------------------------|-----------------|--------------|--------------------------------|--------------|--------------------------|--------------------------------|--------------------------------|--------------------------|
| Procedures   | Screening | Deep
Pheno-
typing | Therapy         | Dose 1 (8 h) | Between
Dose 1 & 2
(2 h) | Dose 2 (8 h) | After
Dose 2
(2 h) | Integration b (2 h) | Deep
Pheno-
typing       | Follow-up 3 and 6 months |
| Visit Number | 1         | 2                        | 3, 4            | 5            | 6, 7                           | 8            | 9                        | 10, 11, and 12                 | 13                             | 14 and 15                |
| Day Number   | Up to -42 | 1 to 7                   | 11 and
18 ±7 | 22 ±3        | 23 and 29 ±3                   | 36 ±3        | 37 ±3                    | 43, 50, and 57
±3           | 64 ±3                          | 120 and
204 ±7        |

AE=adverse event; CPAQ-8=Chronic Pain Acceptance Questionnaire 8; C-SSRS=Columbia Suicide Severity Rating Scale; FM=fibromyalgia; fMRI=functional connectivity magnetic resonance imaging; PGI-C= Patient Global Impression of Change; PI-NRS=pain intensity numeric rating scale; Q=questionnaire; PHQ-8=Patient Health Questionnaire depression scale; PROMIS-29+2=Patient Reported Outcomes Measurement Information System 29-item profile measure plus 2 cognitive functioning items; SAE=serious adverse event; SCID-5=Structured Clinical Interview for Diagnostic and Statistical Manual for Mental Disorders 5th Edition; SCID-5-PD= Structured Clinical Interview for Diagnostic and Statistical Manual for Mental Disorders; WOCBP=women of childbearing potential.

Note: Assessments scheduled on a day of study drug administration should be performed prior to study drug dosing unless otherwise specified.

- a Informed consent must be obtained before any study-specific screening assessments are performed. Screening assessments are to be performed within 42 days preceding Dose 1.
- b The Monitor Rating Form will be used by the same 2 therapists to provide ratings from Dose 1 up to 3 weeks postdose that focus on integration.
- c Participants who do not complete both doses of TRP-8802 will return to the clinic within 28 days after their last dose of study intervention for an End of Therapy Visit.

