## **4.1.6.** End of Therapy (Visit 13, Day 64)

The EOT assessment will occur approximately 28 days after the last dosing session, when participants will complete their final deep phenotyping session. Regardless of whether or not a participant completes both dosing sessions or chooses to discontinue the study early, participants will be asked to complete all EOT and follow-up assessments if they have received at least 1 dose of TRP-8802.

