# 7.2. Participant Discontinuation/Withdrawal from the Study

- A participant may withdraw from the study at any time at his/her own request or may be withdrawn at any time at the discretion of the investigator for safety, behavioral, or compliance reasons. This is expected to be uncommon.
- At the time of discontinuing from the study, if possible, the EOT and follow-up visits should be conducted, as shown in the SoA (Section 1.3). See SoA for data to be collected at the time of study discontinuation and follow-up.
- If the participant withdraws consent for disclosure of future information, the sponsor may retain and continue to use any data collected before such a withdrawal of consent.

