#### 8.1.2. Adverse events

Adverse events will be assessed throughout the study as detailed in Section 8.4.

New onset of suicidal ideation will be considered an AE. Suicidal ideation will be assessed during every in-person visit using the C-SSRS and clinical assessment during participant interviews. The C-SSRS was developed by researchers at Columbia University and is widely used in clinical and research settings (https://cssrs.columbia.edu/). Significant suicidal ideation is endorsed on items 4 or 5 on the C-SSRS.

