## 8.4.1. Time Period and Frequency for Collecting AE and SAE Information

All AEs and SAEs will be collected from the Baseline visit until the EOT visit, at the time points specified in the SoA (Section 1.3). Medical occurrences that begin before Baseline deep phenotyping but after obtaining informed consent will be recorded as Medical History, not as AEs.

All SAEs will be recorded and reported to the sponsor or designee immediately and under no circumstance should this exceed 24 hours, as indicated in Appendix 2, Section 10.2.3. The investigator will submit any updated SAE data to the sponsor within 24 hours of it being available.

Investigators are not obligated to actively seek information on AEs or SAEs after the conclusion of the study participation. However, if the investigator learns of any SAE, including a death, at any time after a participant has been discharged from the study, and he/she considers the event to be reasonably related to the study intervention or study participation, the investigator must promptly notify the sponsor.

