# 8.5. Clinical Safety and Monitoring

At enrollment, potential participants will be appropriately screened for exclusionary psychiatric conditions, medical co-morbidities, and concomitant medications. In addition medical screening will include blood tests including complete blood count (CBC), comprehensive metabolic panel (CMP), urine drug screen (UDS). Subjects with any clinically significant lab abnormalities will be excluded from participation.

Throughout the entire study, suicidal ideation will be assessed during every in-person visit using the C-SSRS and clinical assessment during participant interviews. Significant suicidal ideation is endorsed on items 4 or 5 on the C-SSRS. If the patient screens positive on the C-SSRS at any time during the study, they will undergo a more detailed suicidal risk assessment by study clinician. If they are determined to be at risk of suicide they will be transferred to ED for further Psychiatric evaluation.

During administration, heart rate and BP will be assessed before TRP-8802 capsule administration and at 30, 60, 90, 120, 180, 240, 300, and 360 minutes after capsule administration. Blood pressure and pulse measurements should be preceded by at least 5 minutes of rest for the participant in a quiet setting without distractions (e.g., television, cell phones). If a patient's blood pressure is >200 systolic or >110 diastolic for more than 15 minutes (i.e. 4 consecutive readings) they will be transferred to ED whether or not they are symptomatic.

AEs will be monitored at every study visit. Study staff will also be available throughout the course of the study for emergent AEs. Throughout the administration period, therapists will assess the presence and intensity of participant behaviors, symptoms, and non-verbal cues, which includes questions about the presence/intensity of behaviors, signs, and reported symptoms, such as peacefulness, yawning, nausea/vomiting, quantity of speech, anxiety, sleepiness, crying, restlessness, visual changes, euphoria, and feelings of unreality. They will also complete assessments of mood and safety at the end of the administration sessions.

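### For participants who receive only Dose 1, the EOT visit has a 28-day maximum but no minimum, so a compliant early EOT can end collection of new AEs 7 or 14 days after the dose

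*Combined protocol and SAP*

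**What the plan says.** **When EOT takes place**

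- Section 4.1.6: "The EOT assessment will occur approximately 28 days after the last dosing session". It covers people who miss Dose 2: "participants will be asked to complete all EOT and follow-up assessments if they have received at least 1 dose of TRP-8802".
- Section 4.1.2 also places the end of active intervention 28 days after the final dosing session.
- Table 2, footnote c, is the specific rule for people who miss a dose: "Participants who do not complete both doses of TRP-8802 will return to the clinic within 28 days after their last dose of study intervention". It gives a maximum and no minimum.
- Section 7.2: "At the time of discontinuing from the study, if possible, the EOT and follow-up visits should be conducted, as shown in the SoA". The opening words could mean EOT at the moment of discontinuation. The reference to the Schedule of Activities leads back to footnote c.

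**When AE collection ends**

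- Section 8.4.1: "All AEs and SAEs will be collected from the Baseline visit until the EOT visit". Section 9.4.2 repeats this for the primary endpoint.
- In Table 2 the row "Adverse event reporting" is marked through Visit 13 and blank for Visits 14 and 15.
- Section 8.1.2: "Adverse events will be assessed throughout the study as detailed in Section 8.4". It defers to a section that stops at EOT.
- Section 8.5: "AEs will be monitored at every study visit". This does not fit the blank cells for Visits 14 and 15.

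**The concern.** The end of AE collection is tied to a visit that may be moved earlier for one group only: those who receive Dose 1 and not Dose 2. AEs in the Safety Population are the primary endpoint. Under Table 7 one-dose participants are in that population but not in the Full Analysis Set, which requires two doses, nor in the Per Protocol set drawn from it. Safety is therefore the only planned primary or secondary analysis that they enter.

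Some of them will have stopped for safety reasons, since Section 6.5 bars a second dose after events such as psychosis or hypertension. There is no good reason for their period of asking about new events to be shorter than that of completers. Late events are also relevant to this drug. Section 2.3 describes hallucinogen-persisting perception disorder as lasting weeks to years and possibly appearing after the study, Section 10.2.2 lists it under serious events, and Section 10.1.5 lists it among the stopping rules. Under Section 5.5 a single possibly related Grade 3 event pauses dosing, so one uncollected event could matter to the Safety Review Committee.

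**Working it through.** **Inputs.** Table 2 and Section 4.1.4 give Dose 1 on Day 22, Visit 7 on Day 29, Dose 2 on Day 36 and EOT on Day 64, each ±3 days. Table 2 puts Visit 14 on Day 120. Section 4.1.7 puts the first follow-up 84 days after the final dose.

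**The plan's own figure.** Dose 2 to EOT: 64 − 36 = 28 days, as Section 4.1.6 states. With the windows applied independently: 61 − 39 = 22 to 67 − 33 = 34 days.

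**One-dose participants, two example timings.** The 28-day target falls on Day 22 + 28 = 50. Both timings below are inside the maximum in footnote c.

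| EOT held on | Days after Dose 1 | With windows | Days short of 28 |
|---|---|---|---|
| Visit 7 slot (Day 29, if in person) | 29 − 22 = 7 | 1 to 13 | 21 (75%) |
| Planned Dose 2 day (Day 36) | 36 − 22 = 14 | 8 to 20 | 14 (50%) |

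**Gap to the next scheduled visit.** For someone who has stopped, the visit after EOT is Visit 14.

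- If it is timed from the only dose, it falls on Day 22 + 84 = 106. The gap is 106 − 29 = 77 or 106 − 36 = 70 days.
- If it stays on Day 120, the gap is 120 − 29 = 91 or 120 − 36 = 84 days.

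Even if Section 8.5 overrides the blank cells at Visit 14, no visit falls between the early EOT and day 28.

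**Size across the trial.** The documents give no number of stoppers, and Section 7.1 calls stopping rare. The floor is 0 days. As an assumption, let 1 or 2 of 10 dosed participants stop and have an early EOT.

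- Days lost: 1 × 14 = 14 to 2 × 21 = 42.
- Against the 28 days after the last dose: 10 × 28 = 280 participant-days, so 14/280 = 5% to 42/280 = 15%.
- Against all AE collection from Day 1, with a one-dose participant followed to Day 50: 9 × 64 + 50 = 626 and 8 × 64 + 2 × 50 = 612, so 14/626 = 2% to 42/612 = 7%.

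**Effect on the any-AE percentage.** It is 0 points for a stopper who already has a recorded AE. If a stopper's only AE falls in the lost days, the change is one participant: 1/11 = 9.1 points with ten completers and one stopper, or 1/10 = 10.0 points with ten dosed in all.

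**The case against.** The strongest reply is that the timing rules do not contradict each other. One EOT visit near day 28 satisfies footnote c and Section 4.1.6 together, and Section 4.1.2 supports the same target. A reader might infer two incompatible dates. The documents do not support that; what is missing is a minimum.

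Nor does the protocol schedule an EOT on day 7 or day 14. EOT is a deep-phenotyping visit with sensory testing and imaging, whereas Visit 7 is a two-hour session that may be virtual. The two timings are examples of what the wording allows. It is also reasonable to let EOT be early for someone who is leaving, because that protects the EOT data.

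A reader might further infer that people stopped for safety go unfollowed. They do not. Section 8.4 keeps the investigator responsible for serious events, related events and events that led to discontinuation, and Section 8.4.3 requires active follow-up of reported events. The suicidality scale continues at Visits 14 and 15, staff remain available for emergent events, and under Section 4.4 participation runs to Visit 15. The acute effects described in Section 2.3 (blood pressure, heart rate, headache) arise within hours to a day and are covered by the dosing day and next-day visits.

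All of this stands and narrows the point. It does not close the gap, because none of these provisions requires anyone to ask about new AEs between an early EOT and day 28. Section 7.1 also says that stoppers will not remain in the study, although they are asked to complete assessments, which weakens reliance on continued participation.

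**Conclusion.** The point holds as a minor one. The wording allows a compliant EOT that ends collection of new AEs well before day 28 in participants who receive only Dose 1. The loss is 0 days if nobody stops or if EOT is near day 28. Otherwise it is 14 to 21 days per stopper for the two example timings; footnote c sets no lower limit, so these are illustrations and not bounds. The trial-wide percentages rest on the assumed 1 or 2 stoppers.

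It would be too strong to say that the primary endpoint is compromised. The analysis is a descriptive count and percentage in about 10 participants, and anyone who stopped because of an AE is already counted. What could be missed is a later or additional event in a few people. The reason to act is that these are participants for whom fuller safety information is wanted and that the remedy costs almost nothing.

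**What to change.** In Table 2 footnote c and Section 8.4.1, state: *For participants who receive TRP-8802 but do not complete both doses, EOT is targeted at about 28 days after the last dose. If EOT is held earlier, AEs are collected until 28 days after the last dose by one phone contact at about day 28.* Align Section 9.4.2 with this end point, and limit the statement in Section 8.5 to visits within the AE collection period. Section 7.2 already points to the Schedule of Activities and would follow.

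Two-dose participants keep EOT on Day 64 ±3 as the end of AE collection. Extending a day-28 rule to everyone would trigger calls for completers whose in-window EOT falls 22 to 27 days after Dose 2, with little gain.

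The cost is wording changes in four places and one call per affected participant. An early EOT stays permissible for people who are leaving, so no EOT data are put at risk.

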#### 2. Introduction

Psilocybin 3-[2-(dimethylamino) ethyl]-1H-indol-4-yl] dihydrogen phosphate is a natural product produced by numerous species of Psilocybe mushrooms. The phosphate group is enzymatically cleaved in the body to produce psilocin, an agonist at a variety of serotonin receptors, the most important of which, for its behavioral effects, is the 5-hydroxytryptamine (5-HT)2A receptor (Carhart-Harris 2014; Nichols 2004). Psilocybin was first isolated from Psilocybe mushrooms in 1957, followed by de novo synthesis in 1958 (Passie 2002). It was marketed worldwide in the 1960s as Indocybin™ for experimental and psychotherapeutic purposes. Although it was well tolerated and demonstrated potentially useful effects, it was classified as a controlled substances in the United States and designated as a Schedule I Controlled Substance in 1970; thus, it was effectively removed from clinical use or scientific study.

Psilocybin and similar drugs, such as lysergic acid diethylamide and mescaline, fall into a pharmacological class that are referred to in this application as "classic psychedelics" to differentiate them from other psychoactive substances (3,4 methylenedioxy—methamphetamine [MDMA]) that have different psychological/behavioral effects and different adverse effect profiles and risk/benefit ratios than psilocybin (Carhart-Harris 2013; Nutt 2010). Several lines of evidence suggest that serotonergic hallucinogens, such as psilocybin, have clinical potential for inducing therapeutically beneficial behavior change in patients with a variety of psychiatric conditions (Carhart-Harris 2013). TRP-8802 is being developed for the treatment of FM, other forms of nociplastic pain and overeating disorders.

The pharmacokinetics (PK), pharmacology, and human metabolism of psilocybin are well known and well characterized. Psilocybin has been used as a single agent and as an adjunctive treatment in adult populations. Psilocybin is administered orally and has been studied in openlabel and double-blind, controlled trials. Dosing regimens have ranged from 0.014 mg/kg to 0.6 mg/kg, administered as either a single dose or multiple doses weeks apart (Tryp-8802 Investigator's Brochure [IB]).

Thousands of participants have received psilocybin under controlled conditions in a clinical setting for various indications, with subsequent results published in peer-reviewed journals (Rucker 2017; Metzner 2005). These clinical trials have demonstrated an improvement in symptoms of anxiety, depression, substance use disorder, and other complex neuropsychological conditions. Previous studies in healthy participants have shown oral psilocybin to be well tolerated. No drug- related serious adverse events (SAEs) were reported. Common AEs that were observed after psilocybin administration included cardiovascular (increased blood pressure [BP] and heart rate [HR]), gastrointestinal (nausea, vomiting, and diarrhea), and headache. As these studies were predominantly performed in an academic setting, safety reporting criteria and the level of data verification varied greatly between studies, but these data can be used to elucidate the expected adverse event profile of TRP-8802.

Fibromyalgia is a chronic syndrome of widespread musculoskeletal pain that often manifests with a cluster of co-occurring symptoms, including sleep disturbances, fatigue, cognitive

dysfunction, and mood problems including anxiety and depression. TRP-8802 therapy delivered in concert with psychotherapy may be a safe and effective treatment for symptoms associated with FM. The pressing need for effective FM treatments, the known safety of psilocybin therapy, and the mechanistic plausibility for potential benefit provide a rationale for investigating TRP-8802 therapy as a treatment for FM.

This is an open-label pilot study to assess the clinical benefit of oral TRP-8802 in concert with psychotherapy to treat chronic pain symptoms in patients with FM. Participants will undergo an initial pain phenotyping assessment and will complete a daily electronic pain diary until the end of active intervention. TRP-8802-psychotherapy intervention, the structure of which has been used in previous psilocybin clinical trials, will begin. During the two study drug administration sessions, participants will receive TRP-8802 in a comfortable setting under the guidance of two therapists. Participants will have an in-person study visit the day after each TRP-8802 administration visit to ensure their safety and comfort. Psychotherapy with the same two therapists will occur between and after TRP-8802 sessions with a focus on integration, helping participants gain insight and understanding from the experience. After the final dosing session, participants will undergo 3 weekly integration sessions, and then complete a post-treatment deep phenotyping session. Participants will complete patient reported outcome questionnaires at 84 and 168 days after the final TRP-8802 dose to examine persistence of changes.

## 2.1. Study Rationale

Fibromyalgia is a chronic pain condition that affects 2% to 4% of the population and is characterized by widespread pain as well as a cluster of co-occurring symptoms that include sleep disturbances and cognitive fog. Current treatments for FM are inadequate and there is an unmet need for treatment. Fibromyalgia treatment is challenging: many nonpharmacological therapies are inaccessible due to cost and lack of treatment providers, and most pharmacological therapies are only modestly effective and cause a significant side-effect burden. Some researchers have proposed that psychedelic drugs, such as psilocybin may have potential therapeutic value for treating FM and chronic pain.

Much of this interest has been generated by the results from small clinical trials among individuals with psychiatric disorders such as anxiety, depression, and addiction (Carhart-Harris 2021; Davis 2021a; Carhart-Harris 2018; Johnson 2017; Carhart-Harris 2016; Griffiths 2016; Ross 2016; Johnson 2014; Grob 2011), which show remarkable improvements in otherwise seemingly intractable conditions. Studies with modern neuroimaging techniques (e.g., functional connectivity magnetic resonance imaging [fMRI]) have shown that psilocybin dramatically alters maladaptive patterns of connectivity between different brain regions, which in combination with psychotherapy may promote improved clinical symptoms. Basic science research has identified the serotonin 5-HT2A receptor as the primary target for psychedelics – a finding of interest given that polymorphisms in the encoding 5-HT2A gene are associated with FM and chronic widespread pain (Nicholl 2011; Bondy 1999). While case series and retrospective surveys do suggest that psychedelic use may improve chronic pain due to cluster headache/migraine (Schindler 2015), phantom limb pain (Ramachandran 2018), and nociplastic and neuropathic pain (Castellanos 2020), no studies have examined the potential role of psychedelics in FM.

CONFIDENTIAL 18 27 February, 2024

To better understand the potential benefits of psychedelics in chronic pain management, we are conducting this pilot clinical study with TRP-8802 among individuals with FM. Key procedures have been adapted from other clinical trials using psilocybin (Davis 2020), including psychotherapy sessions for participants to both prepare for and to integrate the TRP-8802 experience after administration.

